7.2. PRO Endpoints

For the PRO endpoints based on IBDQ, CCI [REDACTED] rules suggested by the developers of the questionnaires will be followed in calculating the endpoints with any missing items. If these rules are not sufficient to impute the missing values, then the missing values will be handled as following:

- For IBDQ binary endpoints IBDQ remission and deterioration (worsening) in IBDQ bowel symptom domain, they will be handled in the same way as binary efficacy endpoints as specified in section 7.1 for missing data and data after the dose escalation.
- For IBDQ CCI [REDACTED] continuous endpoints, they will be handled in the same way as continuous efficacy endpoints as specified in section 7.1 for missing data and data after the dose escalation.

CCI [REDACTED]

7.3. Safety Data Endpoints

Safety data will be summarized based on observed-case data. Missing data will not be imputed.

8. STATISTICAL METHODOLOGY AND STATISTCAL ANALYSES

8.1. Statistical Methods

As no formal statistical tests will be conducted, there will be no need to report p-values. Descriptive summary statistics such as number, percentage for categorical endpoints and mean, standard deviation, median for continuous endpoints will be presented, along with some graphical representations using the FAS as defined in [Section 5.1](#).

8.2. Statistical Analyses

8.2.1. Demographic and Baseline Characteristics

Demographics and baseline characteristics will be summarized for the FAS and subpopulations as detailed in [Section 5.3](#) for overall and by initial dose assignment.

8.2.2. Primary Analysis

The primary analysis is the analysis of safety. See [Section 8.2.3](#) below.

8.2.3. Secondary CCI [REDACTED] Efficacy Analyses

All efficacy endpoints are considered as secondary CCI [REDACTED]. Descriptive summary statistics will be reported at scheduled visits in FAS, and subpopulations: maintenance

remission subpopulation, maintenance treatment failure subpopulation, other maintenance completers subpopulation, and induction non-responder subpopulation. However, the endpoints of proportion of subjects with dose increase from tofacitinib 5 mg BID to 10 mg BID will be summarized for maintenance remission subpopulation only.

For FAS or each subpopulation, the data will be summarized based on the following table:

Efficacy Analysis Population/Subpopulation	Treatment group (the default is the assigned dose for initial assignment in A3921139)	By group
FAS	Overall Tofacitinib 5 mg BID Tofacitinib 10 mg BID	Overall
Maintenance Remission subpopulation	Tofacitinib 5 mg BID	Overall By maintenance treatment (4 groups: 10 mg, 5 mg, placebo, 5mg+10mg)
Maintenance Treatment Failure subpopulation	Tofacitinib 10 mg BID	Overall By dose combination received in induction and maintenance (6 groups) and a 7th group of Tofacitinib 10 mg in induction and Tofacitinib 5 mg + placebo in maintenance
Other Maintenance Completers subpopulation	Tofacitinib 10 mg BID	Overall By maintenance treatment (4 groups: tofacitinib 10 mg, Tofacitinib 5 mg, placebo, Tofacitinib 10 mg and 5 mg combined)
Induction Non-responder subpopulation	Tofacitinib 10 mg BID	Overall By Induction treatment (Tofacitinib 10 mg, Placebo)

CCI [Redacted]

- [Redacted]
- [Redacted]
- [Redacted]
- [Redacted]

8.2.4. Safety Analyses

The primary analysis is the analysis of safety.

That is, all safety data will be summarized descriptively by initial treatment group and combined Tofacitinib group of A3921139 in the safety analysis set. The adverse event data will be summarized for entire treatment duration.

A listing of subjects with dose reduction due to PE risk factors will be provided.

Incidence Rates (IR) of Adverse Events of Special Interest will be provided. Confidence intervals (95%) will be computed using exact Poisson method.

In general, IR will be calculated only for discrete (0/1) endpoints determined by adverse event data for events of special interest only. The numerator will be the number of unique subjects with a treatment emergent event as defined above during the interval from the first dose in Study A3921139 to last dose of tofacitinib + 28 days at risk period. The denominator of the incidence rate is person time accruing from the subject's first dose of tofacitinib in Study A3921139 to last dose of tofacitinib + 28 days, or to the date of the first event, whichever occurs earlier. For a subject who died, the time will be the minimum of (the date of the last dose + 28 days, or death date).

However, for mortality, malignancies (excluding NMSC and NMSC) and MACE related endpoints, all events regardless of their onset within 28 days or beyond after the last dose of tofacitinib will be included.

The concept of 28 days is applied to subjects without events that discontinued or completed the study. For ongoing subjects, 28 days will not be added to the exposure.

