- The proportion of subjects in remission at Month 2, Month 12, Month 24 and Month 36. Remission in this study is defined as a Mayo score ≤ 2 with no individual subscore > 1 , and rectal bleeding subscore of 0.
- The proportion of subjects in clinical remission at Month 2, Month 12, Month 24 and Month 36. Clinical remission in this study is defined as a Mayo score ≤ 2 with no individual subscore > 1 .
- The proportion of subjects in partial Mayo score (PMS) remission over time. PMS remission in this study is defined as a partial Mayo score ≤ 2 with no individual subscore > 1 .
- The proportion of subjects who achieve mucosal healing at Month 2, Month 12, Month 24 and Month 36. Mucosal healing is defined as a Mayo endoscopic subscore of 0 or 1.
- The proportion of subjects with total score in Inflammatory Bowel Disease Questionnaire (IBDQ) ≥ 170 over time.

Safety Endpoints

- Incidence and severity of adverse events (AEs).
- Incidence of serious infections.
- Incidence and severity of clinical laboratory abnormalities and change from baseline in clinical laboratory values.
- Incidence of vital sign abnormalities and change from baseline in vital signs.
- Incidence of clinically significant changes in physical examinations from baseline.
- Incidence of electrocardiogram (ECG) abnormalities during treatment.
- Summary of adjudicated safety events (eg, cardiovascular, malignancy, opportunistic infections).
- Proportion of subjects with addition of lipid lowering agents.

Study Design:

This is a Phase 3, multi-center, open-label study in subjects who have completed or demonstrated treatment failure in the maintenance study A3921096, or who were non-responders after completing induction studies A3921094 or A3921095. Approximately 900 subjects are expected to become eligible for the study. This study will continue up to approximately July 2020. Individual subject duration of participation will vary depending on when the subject was enrolled into the study and the end date of approximately July 2020. Therefore, the duration of participation for an individual subject may range from approximately 4 years to more than 7 years. If the study continues beyond year 6 for an individual subject, the investigator should continue to follow the same visit schedule and study procedures outlined during the study visits of year 4.

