2. STUDY OBJECTIVES AND ENDPOINTS

2.1. Objectives

Primary objective:

- To assess the safety and tolerability of long-term tofacitinib therapy in subjects with UC.

Secondary objectives:

- To evaluate the efficacy of long-term tofacitinib therapy in subjects with UC.
- To evaluate the effect of long-term tofacitinib therapy on quality-of-life in subjects with UC.

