6.3. Subject Withdrawal

Should a subject withdraw from active treatment, the subject should complete the procedures listed at the Month 12/ET Visit. After completing the procedures for the early withdrawal visit, the subject should return for a safety evaluation to occur approximately 4 weeks after discontinuing study medication as per the follow-up visit.

Subjects will be withdrawn from the study if any of the following occurs during the study treatment period:

- If a subject who enrolled from the induction studies A3921094 or A3921095 (ie, non-responders) fails to demonstrate clinical response at Month 2. Clinical response is defined by a decrease from the induction study baseline (A3921094 or A3921095) Mayo score of at least 3 points and at least 30%, with an accompanying decrease in the rectal bleeding subscore of at least 1 point or an absolute rectal bleeding subscore of 0 or 1. The endoscopic subscore based on central reading will be used to assess clinical response.
- If rescue therapy is initiated for UC with the exception of oral 5-ASA or sulfasalazine. Rescue therapy includes re-initiation of oral corticosteroid therapy above 10 mg/day of prednisone or equivalent after a subject has achieved steroid-free status during either Study A3921096 or A3921139.
- If a subject undergoes surgery for UC.
- If a subject remains on oral corticosteroids exceeding 15 mg/day of prednisone or equivalent after Month 3.

A subject may be withdrawn from the study for any of the safety concerns as listed in [Appendix 3](#).

Subjects who develop a serious infection during the study, defined as any infection (viral, bacterial, and fungal) requiring hospitalization or parenteral antimicrobials or being classified as a serious adverse event should be withdrawn from the study (see [Section 7.3.10](#)).

All abnormal laboratory events of clinical significance should be followed until the laboratory values have returned to normal or baseline levels (see [Appendix 3](#)). Subjects who meet the discontinuation criteria described in [Appendix 3](#) will be withdrawn from the study.

If a subject has any clinically significant, study-related abnormalities at the conclusion of the study, the Pfizer medical monitor (or designated representative) should be notified and every effort should be made to arrange follow-up evaluations at appropriate intervals to document the course of the abnormalities.

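### SAP 8.2.4 specifies only whole-period incidence rates for events of special interest, so the planned tables cannot show whether risk changes with time on study

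*SAP*

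**What the plan says.** Protocol 2.1 gives the primary objective as "To assess the safety and tolerability of long-term tofacitinib therapy in subjects with UC". The Protocol Summary and Section 3 say that "the duration of participation for an individual subject may range from approximately 4 years to more than 7 years". SAP 8.2.2 makes safety the primary analysis.

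SAP 8.2.4 then sets out the following:

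- **Grouping:** "all safety data will be summarized descriptively by initial treatment group and combined Tofacitinib group of A3921139 in the safety analysis set". Each event of special interest therefore gets three rates: initial 5 mg, initial 10 mg, and combined.
- **Period:** "The adverse event data will be summarized for entire treatment duration".
- **Rate:** the numerator is the number of unique subjects with an event. The denominator is "person time accruing from the subject's first dose of tofacitinib in Study A3921139 to last dose of tofacitinib + 28 days", or time to the first event if earlier. The 95% intervals are exact Poisson.
- **Exception:** for mortality, malignancy and MACE, "all events regardless of their onset within 28 days or beyond after the last dose of tofacitinib will be included".

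The readable text of SAP 6.2, SAP 8.2.4 and Protocol 9.4 specifies no adverse event rate by exposure interval and no time-to-event display. SAP Appendix 1 supplies windows for safety displays shown by visit, but defines no event rate by time. Efficacy, a secondary objective, is summarized visit by visit (SAP 8.2.3).

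**The concern.** A whole-period rate describes early and late risk equally well only if the rate is constant. The design gives several reasons to doubt that it is:

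- Protocol 6.3 lists as a ground for withdrawal: "If a subject who enrolled from the induction studies A3921094 or A3921095 (ie, non-responders) fails to demonstrate clinical response at Month 2".
- Subjects with a serious infection are to be withdrawn (Protocol 6.3 and 7.3.10).
- Subjects in stable remission after 2 consecutive years on 10 mg BID may transfer to Study A3921288 (Protocol Section 3).
- The Amendment 11 pulmonary embolism risk check applies only at visits beyond Month 36, so late exposure was managed differently from early exposure.

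The people at risk in year 5 are thus a selected remainder of those at risk in month 1. If malignancy or MACE risk rose after several years, early person-time would dilute the rise. A change in serious infection risk over time would not show at all. The planned tables could support a statement about average risk on treatment, but not about late risk as distinct from early risk.

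**Working it through.** **1. The plan's own figure.** SAP 4.2.1 expects 460 subjects from maintenance and 440 from induction: 460 + 440 = 900, as stated. The documents give no person-years, event rates or retention figures, so everything below rests on stated assumptions.

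**2. Why one rate cannot show a trend.** Let r be the rate up to Month 36, k times r the rate afterwards, and w the share of person-time after Month 36. Then

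overall rate = r × [(1 − w) + k × w] = r × [1 + (k − 1) × w].

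This is one equation with two unknowns, r and k. As an illustration, take 1785 person-years before Month 36 and 1074 after, a total of 2859. These follow from 900 subjects, 10% per year discontinuing, half of induction entrants leaving at Month 2, and follow-up ending uniformly over 4-7 years. An overall rate of 0.70 per 100 person-years requires r = 0.70 × 2859 / (1785 + k × 1074):

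| k | Early rate | Late rate | Overall |
|---|---|---|---|
| 0.5 | 0.86 | 0.43 | 0.70 |
| 1 | 0.70 | 0.70 | 0.70 |
| 2 | 0.51 | 1.02 | 0.70 |
| 3 | 0.40 | 1.20 | 0.70 |

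The ambiguity does not depend on the retention assumption; only its size does.

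**3. Size of w.** With k = 2 the overall rate rises by exactly w. Person-years = 900 × ∫ exp(−ht) × G(t) × W(t) dt, where:

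- h is a constant discontinuation rate per person-year (assumed);
- G is 1 to year 4, then falls linearly to 0 at year 7.5 (assumed, from the stated range of about 4 to more than 7 years);
- W is 1 to Month 2, then 1 − m × 440/900, with m the fraction of induction entrants leaving at Month 2 (assumed).

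| h | m | Total person-years | Beyond Month 36 | w |
|---|---|---|---|---|
| 0 | 0 | 5175 | 2475 | 47.8% |
| 0.05 | 0.5 | 3422 | 1491 | 43.6% |
| 0.10 | 0.3 | 3358 | 1346 | 40.1% |
| 0.20 | 0.3 | 2621 | 867 | 33.1% |
| 0.30 | 0.5 | 1880 | 499 | 26.5% |

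The first row can be checked by hand: mean follow-up is (4 + 7.5)/2 = 5.75 years, and (5.75 − 3)/5.75 = 47.8%. If 30% is read as the proportion lost each year (h = −ln 0.7 = 0.357), w falls to about 23%. Other end dates widen the range. If everyone is followed exactly 4 years with 30% lost per year and half of induction entrants leaving at Month 2, w is about 13%. If everyone is followed 7 years with no loss, w = 4/7 = 57%.

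**4. What interval rows would show.** Use the 1785 and 1074 person-years of step 2 and assume a true rate of 0.5 per 100 person-years, doubling after Month 36. Expected events are 1785 × 0.005 = 8.9 and 1074 × 0.010 = 10.7. With 9 and 11 events and exact Poisson intervals:

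- to Month 36: 0.50 (0.23-0.96) per 100 person-years;
- beyond Month 36: 1.02 (0.51-1.83);
- overall: 20/2859 = 0.70 (0.43-1.08).

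The split points in the right direction, but the intervals overlap. On the step 3 model with h = 0.10 and m = 0.5 (1798 and 1192 person-years, about 9 and 12 events), an exact conditional two-sided 5% comparison of the two periods would detect the doubling about 28% of the time. With h = 0.30 and m = 0.5 (1381 and 499 person-years) it would do so about 15% of the time.

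**The case against.** The best reply is that nothing planned is contradicted. The safety endpoints are incidences, no hypothesis is tested, and neither document promises an early-versus-late comparison. A person-time average over several years of treatment is a valid answer to a question about the safety of long-term therapy. That stands: a reader might infer that the planned rate is invalid unless risk is constant, and it is not. It is simply silent on time.

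The benefit of splitting is also limited, as step 4 shows. Many narrow intervals would leave a handful of events in each. Splitting does not remove selection, because a falling infection rate after susceptible subjects have withdrawn still cannot be told from a true decline. Time since first A3921139 dose is not total tofacitinib exposure either, since entrants come from induction or maintenance and from active drug or placebo. These points stand, and they argue for few intervals and cautious wording.

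A naive split would also distort the events of most interest. For mortality, malignancy and MACE, events are counted however late they occur, while person-time stops at last dose + 28 days. A malignancy at Month 40 in someone who stopped at Month 10 would enter a late row without any matching person-time. The fix has to deal with this.

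Finally, part of SAP 6.2 is redacted, and Protocol 9.4 defers to sponsor standards that are not among the documents. Ongoing DSMB review of accumulating safety data covers emerging signals in part, but does not replace a display in the final report.

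**Conclusion.** The point holds as a gap in the readable text: the rates for events of special interest are whole-period only, so the tables cannot show whether risk changes with time on study. Under a discontinuation rate of 0.10-0.30 per person-year and follow-up ending uniformly over 4-7.5 years, a doubling after Month 36 would raise the overall rate by about 26-40%, or by up to about 48% with no discontinuation.

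Three stronger readings are not supported:

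- A reader might infer a single rate per event. SAP 8.2.4 gives three, though neither dose group nor the total separates early from late exposure.
- A reader might infer that the first three years dominate the person-time. The documents give no retention data, and across the assumptions tried that share runs from 43% to 87%. More than half is likely, but it is an assumption.
- A reader might infer that thromboembolism is among the rates affected. The readable text of SAP 8.2.4 names mortality, malignancy and MACE, but does not name thromboembolism as an event of special interest.

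This is a worthwhile, inexpensive improvement rather than an error in the planned rates.

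**What to change.** In SAP 8.2.4, keep the overall rates as the summary. For each event of special interest, add the incidence rate with exact Poisson 95% interval in two or three intervals since first A3921139 dose, for example 0-12, >12-36 and >36 months. Show subjects at risk, first events and person-years for each interval.

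For mortality, malignancy and MACE, count in the interval rows only events up to last dose + 28 days, so that numerator and person-time match. Report later events separately. The overall rates for these events stay as now defined.

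State in the SAP that the rows are descriptive, that withdrawal-driven selection remains, and that time since first A3921139 dose is not total tofacitinib exposure.

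The cost is one more table per event from data already held, with no new data collection and no hypothesis test. The price is wide late intervals, such as the 0.51-1.83 per 100 person-years shown above for 11 events, and some risk that readers over-interpret noise, which the descriptive label should limit.

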withdrawals due to treatment failure in Study A3921096 are eligible to receive tofacitinib 10 mg BID. Treatment failure is defined by an increase in Mayo score of at least 3 points from the baseline value of the maintenance study (A3921096), accompanied by an increase in rectal bleeding subscore by at least 1 point, and an increase of endoscopic subscore of at least 1 point (yielding an absolute endoscopic subscore of ≥ 2) after a minimum of 8 weeks of treatment in the maintenance study. In the scenario where the endoscopic subscore is a '3', and the maintenance baseline endoscopic subscore is already a '3' (maximum value), then an increase by at least 1 point will not be needed in order to meet treatment failure. However, all other components of the treatment failure criteria will still need to be met. Subjects who complete induction Study A3921094 or A3921095 and are classified as non-responders are also eligible to receive tofacitinib 10 mg BID.

Tofacitinib dose can be adjusted from 5 mg BID to 10 mg BID for efficacy and from 10 mg BID to 5 mg BID after meeting specific laboratory abnormalities or other protocol defined criteria regarding efficacy. Dose adjustments can only occur after a subject has received at least 8 weeks of treatment in Study A3921139.

Subjects from the induction Study A3921094 or A3921095 (ie, non-responders) who fail to demonstrate clinical response at Month 2 of this study will be withdrawn from the study. Clinical response is defined by a decrease from the induction study baseline (A3921094 or A3921095) Mayo score of at least 3 points and at least 30%, with an accompanying decrease in the rectal bleeding subscore of at least 1 point or an absolute rectal bleeding subscore of 0 or 1. The endoscopic subscore based on central reading will be used to assess clinical response.

Subjects who enroll into this study, who are on tofacitinib 10 mg BID for at least 2 consecutive years, and who are in stable remission on tofacitinib 10 mg BID for at least 6 months may have the opportunity to enter Study A3921288 (A Phase 3b/4, Multi-Center, Double-Blind, Randomized, Parallel Group Study of Tofacitinib in Subjects with UC in Stable Remission) if they meet the eligibility criteria. These subjects must:

- Have received tofacitinib 10 mg BID for a minimum of 2 consecutive years in Study A3921139 (and not have their tofacitinib dose reduced to 5 mg BID due to safety or efficacy).

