- Be in stable remission on tofacitinib 10 mg BID for the 6 month period in Study A3921139 up to and including the baseline visit of Study A3921288, defined as meeting all the following criteria:
 - A partial Mayo score ≤ 2 , with no individual subscore > 1 and a rectal bleeding subscore of 0 at each study visit during the 6 month period in Study A3921139 prior to and at baseline of Study A3921288; AND
 - At least one assessment of remission based on Mayo score.
- Not be receiving any corticosteroids to treat their UC for at least 4 weeks prior to the baseline visit of Study A3921288.

[figure not shown]
Study A3921288 will evaluate the efficacy and safety of tofacitinib in subjects in stable remission on 10 mg BID who decrease the dose to and remain on 5 mg BID compared to subjects who remain on 10 mg BID.

All subjects who withdraw early or who complete this open-label study, with the exception of those subjects entering Study A3921288, will have a 4-week safety follow-up evaluation after the last dose of study medication.

Subjects will be required to remain on stable doses of their concomitant medications for UC during the study period. Subjects who enter this study on corticosteroids (eg, subjects who withdraw from Study A3921096 due to treatment failure or non-responders at the end of Study A3921094 or A3921095) will need to continue the steroid tapering regimen described in Study A3921096. If a subject requires rescue therapy or undergoes surgery, the subject should be withdrawn from the study and appropriate agents should be given at the discretion of the investigator.

Per protocol Amendment 11, Version 18 June 2019, the study investigator or designee will be required to ask each subject at each study visit if he/she has any newly-developed risk factors for PE, and if one is identified, the subject will need to have their tofacitinib dose adjusted to 5 mg BID if they are taking open label 10 mg BID.

Figure 1. Study Design

- Study visits will occur every 3 months after the first year until approximately July 2020.
- All subjects will have a 4-week follow-up evaluation after their last dose of study medication.

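### SAP 8.2.4 limits exposure-based rates to events of special interest, so overall categories such as any SAE default to crude percentages with no common length of follow-up

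*SAP*

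**What the plan says.** SAP 8.2.4 is the primary analysis. It provides that "all safety data will be summarized descriptively by initial treatment group and combined Tofacitinib group of A3921139 in the safety analysis set", and on the time span: "The adverse event data will be summarized for entire treatment duration". For categorical endpoints, SAP 8.1 names the form of summary: "Descriptive summary statistics such as number, percentage for categorical endpoints".

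Person-time rates appear in two sentences of 8.2.4. The first is "Incidence Rates (IR) of Adverse Events of Special Interest will be provided". The second sets the scope: "In general, IR will be calculated only for discrete (0/1) endpoints determined by adverse event data for events of special interest only". The section then defines the numerator (unique subjects with an event), the person-time (first dose to 28 days after the last dose, or to the first event) and an exact Poisson 95% interval. Mortality, malignancy and MACE are clearly covered.

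On follow-up, SAP 2.1 says that induction non-responders "who fail to demonstrate clinical response at Month 2 of this study will be withdrawn from the study". It also allows a move to Study A3921288, for which subjects must "Have received tofacitinib 10 mg BID for a minimum of 2 consecutive years in Study A3921139". Subjects who stay may take part for about 4 to more than 7 years. Protocol 4.3 assigns 5 mg BID to subjects in remission at baseline and 10 mg BID to everyone else. SAP 4.2.1 expects about 440 of 900 subjects to come from the induction studies.

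**The concern.** A crude percentage mixes risk with length of observation. One dose column here combines subjects observed for about three months with subjects observed for years, and the mandatory Month 2 exit applies only to subjects who start on 10 mg BID. The combined column has the same mixture. The rows affected are the ones a safety reader usually looks at first: any SAE, any severe AE, any AE leading to discontinuation. No visible passage plans a rate or a time-to-event summary for them.

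The SAP already accepts the person-time principle for events of special interest and already contains the definitions. What is at stake is whether the overall rows of the primary analysis can be interpreted, and whether rates for them are fixed in advance or chosen after open-label data have been seen.

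**Working it through.** The plan states no event rate or precision to reproduce. Its expected size is consistent: 460 + 440 = 900.

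**Who can leave early.** The Month 2 rule applies only to induction non-responders, all of whom start on 10 mg. The A3921288 exit depends on two consecutive years on 10 mg in this study, not on the initial dose. A subject who starts on 5 mg and is escalated under Protocol 5.8 is not excluded by that criterion. This exit therefore affects mainly, but not only, the initial 10 mg group.

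**An offset.** Induction non-responders enter at Week 9 of their parent study and remission subjects at Week 52/53 of the maintenance study. The calendar end is common (about July 2020), so continuing induction entrants can stay longer.

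**Illustration.** From the documents: 440, 900, the 28-day period, and Day 60 as the Month 2 target (SAP Appendix 1). Everything else is assumed: 160 subjects on 5 mg; 740 on 10 mg (440 + 300); a share w = 30%, 45% or 60% of the 440 leaving at Month 2; maximum stay T = 4 years for the others; dropout 0, 5 or 10% per year; the same true first-event rate r = 5, 8 or 12 per 100 person-years (PY) on both doses.

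With g = 28/365.25 and d = -ln(1 - annual dropout):

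- Staying subjects: c(T) = 1 - exp(-r g) × {[d/(d + r)] × [1 - exp(-(d + r)T)] + exp(-(d + r)T)}
- Month 2 leavers (60 + 28 = 88 days): s = 1 - exp(-r × 88/365.25)
- 5 mg: c(T)
- 10 mg: [440w s + 440(1 - w) c(T + a) + 300 c(T)]/740, where a is the extra stay of induction entrants

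Worked case: r = 0.08, no dropout, w = 45%.

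- c(4) = 1 - exp(-0.08 × 4.077) = 27.8%; s = 1.9%; c(5) = 33.4%
- a = 0: (198 × 0.0191 + 542 × 0.2783)/740 = 20.9%; ratio 0.75
- a = 1: (198 × 0.0191 + 242 × 0.3338 + 300 × 0.2783)/740 = 22.7%; ratio 0.82

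The true rate ratio is 1 in both. Over the whole grid:

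| Scenario | 10 mg/5 mg ratio of crude percentages |
|---|---|
| Equal dropout, equal maximum stay | 0.67-0.84 |
| Equal dropout, induction entrants stay 1 year longer | 0.71-0.92 |
| As above, and half of the other 10 mg subjects stay 6 months longer | 0.72-0.95 |
| Induction entrants 1 year longer; dropout 15%/yr on 5 mg, 5%/yr on 10 mg | 0.85-1.11 |

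With equal dropout and the extra year, the direction also reverses if fewer than about 13-19% of induction entrants leave at Month 2.

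**Combined column.** At r = 0.08, with the extra year for induction entrants, the combined percentage is 17.5-25.9% for a 4-year maximum and 23.4-38.7% for a 7-year maximum. The underlying rate is the same throughout.

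**Risk period for AEs leading to discontinuation.** Such an event cannot occur after the last dose, so the added 28 days carry no risk. At 5 per 100 PY, with 0 or 10% yearly dropout and the extra year, those days make up 1.9-3.2% of counted person-time on 10 mg and 1.7-2.1% on 5 mg. The effect is small but unequal between the groups.

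**The case against.** The strongest objection is that the default to percentages is inferred. The SAP names no table for any SAE, any severe AE or any AE leading to discontinuation. The list in 8.1 is open-ended, and the scope sentence for rates begins with a qualifier. Part of SAP 6.2 is redacted, Protocol 9.4 refers to data standards that are not shown, and the list of events of special interest cannot be read. This stands as a limit: the point holds on the visible text only. It does not remove the point, because the one explicit scope rule restricts rates, and the SAP's change log describes the 6.2 update in the same terms. Latitude in the wording is also not prespecification.

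A second objection is that the numbers rest on assumptions, and that equal dropout is doubtful in groups chosen for opposite disease status. This stands for the size and direction by dose. It does not touch the missing common follow-up length, which follows from the design.

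A third is that no hypothesis is tested and dose follows remission status, so the dose comparison is confounded whatever is reported. That is correct. Rates repair follow-up length only.

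A reader might infer that the crude tables will make 10 mg look safer. The documents do not support this: that group holds subjects with more active disease, its true rate may be higher, and dropout could reverse the direction. A reader might also infer that serious events get no rates at all, but mortality, malignancy and MACE do. Nor is the A3921288 exit closed to subjects who started on 5 mg.

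**Conclusion.** The point holds on the visible text, as a cheap improvement to the primary analysis. Crude percentages for the overall safety categories would refer to no common length of observation, by dose or combined. That conclusion needs only the Month 2 rule, the 440 of 900 and the planned 4 to more than 7 years.

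The size by dose is illustrative: at equal true rates, a crude ratio of about 0.67-0.95 with equal dropout, and up to about 1.1 with higher dropout on 5 mg. It rests on assumed group sizes, Month 2 withdrawal, dropout, entry times and a constant event rate. No direction should be claimed for the actual tables.

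**What to change.** Amend both rate sentences in SAP 8.2.4 so that their scope becomes events of special interest plus any SAE, any severe AE and any AE leading to discontinuation. Show the rates with exact Poisson 95% intervals beside number and percentage, by initial dose and combined. There is no need to extend them to every AE term.

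- **Any SAE and any severe AE:** use the numerator and person-time already in 8.2.4.
- **Any AE leading to discontinuation:** end person-time at the last dose or the first event, without the 28 days.
- **Footnote:** the rates adjust for follow-up length only, not for non-random dose assignment or dose switching.
- **If the redacted part of SAP 6.2 or the data standards in Protocol 9.4 already require these rates:** remove the conflicting restriction in 8.2.4 and say so there.

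The cost is SAP wording and three extra table rows from data already collected. There are two small side effects. First-event rates are slightly sensitive to early clustering: with a hazard 2-3 times a baseline of 5 per 100 PY in the first three months, equal hazards give a rate ratio of 1.005-1.067, against a crude ratio of 0.69-0.93. Also, all who withdraw or complete, "with the exception of those subjects entering Study A3921288, will have a 4-week safety follow-up evaluation", so for A3921288 entrants the added 28 days are counted without that visit. For an assumed 50-150 entrants this is 50 × 28/365.25 = 3.8 to 150 × 28/365.25 = 11.5 PY, under 1% of 10 mg person-time in the illustration.
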